### 7.2. Statistical Methods

The endpoint for Complete Protection Time will be time to treatment failure for each subject test. Treatment failure is the time at which the product no longer provides complete protection, which is determined as the time at which the first confirmed landing occurred. First confirmed landing is a landing that is followed by another landing within a 5-minute exposure period, or a landing in an exposure period immediately followed by an exposure period in which a landing occurred. The times to treatment failure will be analyzed using Kaplan-Meier Survival functions, and from these the median Complete Protection Time and 95% confidence intervals (CI) will be calculated. The 95% CI of the estimated mCPT will be calculated with the log-log transformation applied to survival function and Kaplan-Meier survival curves will be presented in the study report.

A first confirmed landing occurring within the first 3 consecutive exposure periods will be considered as 0 for statistical purposes.

Participants that withdraw before the start of testing will be replaced with alternates. Participants that withdraw during the test day will have their data included in the statistical analysis as right censored data. Right-censored data are those data that, despite monitoring of the outcome event, the event does not occur within the study duration or because the participant has withdrawn. Withdrawn subjects whose data are right censored should not be replaced. If 3 or more participants on an individual test day withdraw before they record treatment failure, the Study Director will make the decision as to whether to continue testing and include these right-censored values in the analysis, or end the test day, and attempt a repeat at a later date. In this case the data will be reported, but not included in statistical analysis. The decision, and reasons to continue or discontinue testing, will be recorded.

Adverse events will be tabulated and included in the study report. Adverse events occurring after the end of subject participation but before the end of the study will be listed separately.

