## Study Synopsis

Sponsor:	Livful Inc.
Study Title:	Field Evaluation of two topically applied insect repellent products containing IR3535 against mosquitos in Louisiana.
Short Title:	Louisiana Mosquito Field Trial 1215
ARCTEC Ref:	1215
LSU IRB Approval Date:	
Study Director:	[name]
Test Facility Manager	[name]
Quality Assurance:	Compliance Services International
Monitor:	[name], ARCTEC, LSHTM, [name]
Objective:	To determine the efficacy and duration of protection of two topically applied insect repellent products at preventing landing by mosquitos. The study will follow the EPA Product Performance Test Guidelines  . It is intended to test the products against natural populations of mosquito species of public health importance within the genera Aedes , Anopheles , and Culex , and to replace data from one site previously tested in Florida with data from a site in Louisiana with adequate landing pressure from target mosquito species of public health relevance.
Study Design / Methodology:	A single-site field setting study using healthy volunteers to test two insect repellent product formulations (lotion, and wipe) against mosquitos.  Subjects will have repellent applied to one lower limb at a standardised dose rate to account for skin area. They will then expose this area only in a field site where mosquitos are recorded landing at a rate of 5 mosquitos per 5 minute or higher. The exposure period will last five minutes and all mosquitos landing on the exposed skin will be collected using an aspirator. 5 minute exposure periods will be repeated every half hour for 14 hours for the lotion and 13 hours for the wipe, or until median CPT can be established by more than half of subjects reaching treatment failure.
Number of Subjects:	Based on power analysis, a sample size of 13 test subjects for each product in this study design would provide sufficient power (>0.90) to obtain a ratio of the lower limit of 95% CI of the estimated median CPT / estimated median CPT is $\geq 0.6$ , where the ratio of the lower limit of 95% CI of the estimated median

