#### **4.4. Withdrawal Criteria**

Subjects will be told that they can withdraw at any time without giving a reason for withdrawing and without forfeiting benefits based on their participation prior to withdrawal.

Subjects will be told that they have the option to request their data not be used if they decide to withdraw from the study or if they are withdrawn. Subjects who withdraw from the study or are withdrawn by the Study Director will be notified at the time of the withdrawal that their data will be used unless they request otherwise. Data collected to the point of withdrawal will be used in the analysis of the study unless the subject requests otherwise, in which case it will be removed from the database

Subject's enrollment in the study may be ended at the discretion of the Study Director, where continued participation may affect the safety of the subject or where there is a development of any condition that might interfere with study participation. Withdrawal criteria include:

[figure not shown]
- The Study Director decides that continuing the study would be harmful to the subject.
- The subject is not following directions necessary for the study to proceed.
- Participation in the study has a bad effect on the subject.
- The study is cancelled.

If a subject withdraws during the test day, the Study Director or appropriately trained study staff member will be responsible for ensuring that they are safely returned to their own vehicle or other transport by the end of the test day. If the subject withdraws because they require medical treatment, the Study Director or appropriately trained study staff member will be responsible for ensuring that they are safely returned to their own vehicle, other transport or a medical facility as soon as possible.

At the end of the consenting and screening meeting, unscented soap will be posted to enrolled subjects or made available for collection from the Test Facility.

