## 7. Statistics and Data Analysis

### 7.1. Sample Size Calculation

EPA statisticians used a Weibull distribution to simulate the sample size required to estimate the median CPT to a given degree of precision. A power analysis of these outputs resulted in a sample size of 13 subjects being chosen. This number allows for over 90% power at a range of expected median CPTs from 2-8 hours (Appendix 4: Sample size calculation).

This sample size is appropriate to achieve at least 90% power that the ratio of 95% LCL mCPT/mCPT  $\geq$  0.6), given that the P5MR (i.e., CPT5th percentile/mCPT) is assumed to be equal or greater than 0.5. The assumption for the variation of CPT data distribution is characterized by the value of P5MR, associated with the selected sample size and the result of power. The P5MR value characterizes the spread of the CPT data distribution. For two products with same mCPT, the product with lower value of P5MR has a wider range of CPT data.

To maintain gender balance among the volunteers, at least 6 volunteers of each sex will be recruited to test each product. An additional 2 subjects will be required to act as untreated controls. Five alternate subjects will be invited to take part in each study day. Subjects will be able to take part in one or both test days. Therefore, a minimum of 20, and a maximum of 40 subjects will be required to complete the trial.

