## 11.4. Appendix 4: Sample Size Calculation

### Objective

To determine the sample size N such that the proposed IR3535 mosquito repellency study has sufficient power to obtain a given degree of **precision** in the estimate of Median Complete Protection Time (mCPT). This precision – designated as “K” -- will be expressed by 95% LCLmCPT/estimated mCPT

The simulation used to estimate varying sample sizes will require that that 95% LCLmCPT/estimated mCPT < K, given the true **variation** of the Complete Protection Time (CPT) distribution, expressed by a the Weibull distribution family and a parameter, P5MR, defined as the 5th percentile/mCPT.

**Additional Details:** Two important considerations in developing an estimate of the CPT as a measure of repellency are the **precision** of the estimate and the **variability** of CPT in the population. The precision of the estimate -- designated as “K” -- is defined here as follows:

$$K = 95\% \text{ LCL}_{\text{mCPT}} / \text{estimated mCPT}$$

Where: mCPT= median protection time

95% LCLmCPT = 95% lower confidence limit on mCPT

The degree of variation of the mCPT distribution will be defined as the P5MR which is defined here as the ratio between the mCPT of the 5th percentile of the population to the Median CPT (mCPT) of the population:

$$\text{P5MR} = \text{CPT}_{5^{\text{th}} \text{ \%ile}} / \text{mCPT}$$

Where:

mCPT= median protection time

CPT5th %ile = 5th percentile of the distribution of CPT

The simulation performed by EPA estimates the power of a mosquito repellency study design as a function of the following parameters:

- Sample size
- (Required) precision K of estimated mCPT
- mCPT
- P5MR

Table 1 below presents the power estimates from simulations in which the data were randomly generated from Weibull distributions for K = 0.6. These are shown for various values of mCPT (ranging from 2 to 8 hours), P5MR (ranging from 0.2 to 0.8), and Sample Size (ranging from 10 to 20). Note that K reflects the precision of the estimate of mCPT. For example, the K value of 0.6 requires that the 95% LCL on a median protection of 10 hours be no less than 6 hours while a K value of 0.8 requires that the

95% LCL on that same median protection time be no less than 8 hours. The K of 0.8, then, requires a more precise estimate of the MPT than a K of 0.6.

Full tables and graphs of the simulations are available in trial files.

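### At P5MR 0.5, the stated power of at least 90% has a margin of only 1 to 4 points and no reserve for an early test-day withdrawal, though such subjects are not replaced

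*Protocol*

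**What the plan says.** The synopsis states that "a sample size of 13 test subjects for each product in this study design would provide sufficient power (>0.90"). Section 7.1 repeats the claim: "This number allows for over 90% power at a range of expected median CPTs from 2-8 hours", and "This sample size is appropriate to achieve at least 90% power" that the lower 95% limit of the median is at least 0.6 of the estimated median, where P5MR "is assumed to be equal or greater than 0.5". The figures come from Appendix 4 Table 1, whose simulation varies sample size, required precision, median and P5MR. Withdrawal is not among those parameters.

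Section 7.2 sets the withdrawal rules. Alternates replace subjects who leave before testing starts. Subjects who leave during the test day are kept as right-censored, and "Withdrawn subjects whose data are right censored should not be replaced". A decision by the Study Director is called for only at three or more withdrawals before failure. Under Section 4.4 a withdrawn subject may ask that the data not be used, "in which case it will be removed from the database".

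**The concern.** The power claim is worded as a property of the design for every P5MR from 0.5 upward, so it has to hold at 0.5. The design accepts one or two test-day losses without action, on outdoor days of up to 14 hours for which the protocol's own risk table lists fatigue and heat. If the margin at 0.5 is smaller than the cost of one early loss, the figure used to justify the sample size is a best case at that boundary and is not labelled as one. Only the stated precision is at stake. The analysis method is not in question.

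**Working it through.** **Inputs.** From Sections 7.1 and 7.2 and Appendix 4: 13 subjects; Weibull protection times; success when the lower limit divided by the median is at least 0.6; Kaplan-Meier median with a two-sided 95% log-log interval. From Section 6.7: landing collections start 2 h after application, and the test ends once more than half of the subjects have failed.

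**Step 1: the plan's figure.** The Weibull shape follows from P5MR: shape = ln[ln(1/0.95)/ln 2] / ln(P5MR). At P5MR 0.5 this is ln(0.0740)/ln(0.5) = 3.76. Simulating 13 complete times on a continuous scale gives about 0.90 at medians of 4 and 8 h. Rounding to the nearest half hour gives 0.903 and 0.905, and rounding up gives 0.940 and 0.926. Table 1 has 0.921 and 0.914. The table is therefore reproduced to within about 2 points; its time grid is not stated.

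**Step 2: one subject lost entirely.** This can be read from Table 1 at P5MR 0.5.

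| Median (h) | n=13 | Margin over 0.90 | n=12 | Fall |
|---|---|---|---|---|
| 2 | 0.942 | 0.042 | 0.802 | 0.140 |
| 4 | 0.921 | 0.021 | 0.730 | 0.191 |
| 6 | 0.914 | 0.014 | 0.729 | 0.185 |
| 8 | 0.914 | 0.014 | 0.732 | 0.182 |

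**Step 3: why the fall is so steep.** With d failures out of n and no censoring, S = (n−d)/n, the Greenwood sum is d/[n(n−d)], and the log-log lower bound is S raised to exp(1.96·√Greenwood/|ln S|). The lower limit of the median is the first failure time at which this bound is 0.5 or less.
- n=13, d=2: S = 0.846, Greenwood 0.01399, bound 0.512. Still above 0.5.
- n=13, d=3: S = 0.769, Greenwood 0.02308, bound 0.442. The limit is the 3rd failure time.
- n=12, d=2: S = 0.833, Greenwood 0.01667, bound 0.482. The limit is the 2nd failure time.

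Losing one subject thus moves the lower limit back by one whole failure.

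**Step 4: one subject censored instead of lost.** The documents give neither a withdrawal rate nor a timing, so the timing is an assumption. Simulation at P5MR 0.5 with one of 13 censored gives:
- before any failure (continuous times, medians 4 and 8 h): 0.75 and 0.76, in effect n=12;
- uniformly between 2 h and the median, times to the nearest half hour: about 0.83 to 0.89 over medians of 4 to 8 h;
- the same window, times rounded up: about 0.91 at 4 h, 0.86 at 6 h and 0.85 at 8 h;
- at 75% of the median: 0.89;
- at the median: 0.90, no loss from the continuous-time baseline of 0.90.

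**Step 5: the rest of the permitted range.** With n=12, Table 1 gives 0.943, 0.899, 0.906 and 0.906 at P5MR 0.6, and 0.955, 0.986, 0.988 and 0.989 at P5MR 0.7 (medians 2, 4, 6, 8 h). At P5MR 0.8 it gives 0.987 or more at medians of 4 to 8 h. One censored between 2 h and the median at P5MR 0.6 leaves about 0.95 to 0.98.

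**Step 6: complete data at a median of 2 h.** With all 13 subjects, Table 1 gives 0.875 at P5MR 0.7 and 0.666 at P5MR 0.8. Of the 16 cells with P5MR from 0.5 to 0.8, 14 reach 0.90 at n=13 and 10 at n=12.

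**The case against.** The strongest reply is that Section 7.1 states power conditionally on 13 subjects, that censoring without replacement is ordinary Kaplan-Meier practice, and that the design already limits the damage. Alternates cover losses before testing, a censored subject still contributes information, and the stop once more than half have failed makes later withdrawals irrelevant. The documents give no withdrawal rate for a one-day test. At an assumed 2 to 5% per subject, average power moves by only about 0 to 2.5 points. All of this stands, and it keeps the point small. It does not remove it: at P5MR 0.5 the margin at medians of 4 to 8 h is itself only 1.4 to 2.1 points, and the claim is made for that value.

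A reader might go further and infer that 90% holds only if nobody withdraws, so that any single withdrawal breaks it. The documents do not support that. Step 5 shows about 90% or more with a subject wholly lost at P5MR 0.6 and 0.7, both inside the stated assumption, and late withdrawals cost almost nothing. The converse fails too: Step 6 shows cells below 0.90 with all 13 present. Nor does Appendix 4 say that all 13 simulated subjects contribute a failure time. It only names no withdrawal parameter.

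A reader might also infer that more subjects should be enrolled. Table 1 is not monotone in sample size: at P5MR 0.5, n=15 gives 0.888, 0.873 and 0.875 at medians of 4, 6 and 8 h, below the values for n=13. Adding one or two subjects is therefore no simple remedy.

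**Conclusion.** The point holds in a limited form. At P5MR 0.5 the 90% claim has 1 to 4 points of margin and no reserve for an early test-day loss. If one subject's data are removed, power is 0.73 to 0.80; this comes from the protocol's own table and needs no simulation. If one subject is censored between 2 h and the median, power is roughly 0.83 to 0.91 at medians of 4 to 8 h. That range depends on the assumed timing and on a half-hour grid the protocol does not specify. Separately, at a median of 2 h the sentence in 7.1 is contradicted by Table 1 at P5MR 0.7 and 0.8, even with complete data. The stated figure needs correcting; the sample size and the withdrawal rules can stay as they are.

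**What to change.** Reword the power statement in the synopsis and Section 7.1 along these lines:
- With 13 treated subjects and no loss before the median, Table 1 gives power of 0.91 to 0.94 at P5MR 0.5 for medians of 2 to 8 h.
- If one subject's data are lost, power at P5MR 0.5 falls to 0.73 to 0.80.
- Any figure for a censored withdrawal is given as a range, with its timing assumption stated and starting no earlier than 2 h after application, since alternates replace subjects who leave before testing.
- At least 90% is not claimed for all P5MR of 0.5 or more at a median of 2 h; the values 0.875 (P5MR 0.7) and 0.666 (P5MR 0.8) are cited.

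The cost is a few sentences of protocol text and a less favourable headline figure. Enrolment, conduct and analysis do not change.

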## 8. Safety Reporting and Data Monitoring

### 8.1. Medical Monitor

The medical monitor will be familiar with the protocol prior to the start of the study. They will be available via email and telephone for the study team to consult in cases where inclusion and exclusion criteria maybe unclear. In the case of adverse events, they will be asked to review the information provided and determine the severity and relatedness of the event. Quality assurance will review the use of the medical monitor, and if appropriate may communicate directly with them.

The medical monitor will be Lake Line Direct, a 24 - Hour Nurse Advice and Health Information service available on [contact] or [name] (toll free).

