#### **8.4. Compensation Due to Adverse Events**

If a subject is injured or becomes ill as a direct results of his or her participation in this study, the Sponsor will pay for all reasonable and necessary medical expenses required to treat the injury, as long as:

1. The injury or illness occurs during the subject's participation in the study, and
2. The injury or illness results directly from the test substance or study-related procedures.

If an insect tests positive for a pathogen, then the subject that this mosquito was aspirated from will be contact and informed of the result and advised to consult with a medical practitioner. All other subjects will be notified of the result and recommended to seek medical assistance if they feel ill.

The Sponsor, Medical Monitor, and Study Director will determine whether the injury is related to the subject's participation in the study. To do this, they may request to consult with the person/facility that provided medical treatment following an adverse event, which could require the subject's consent.

No additional compensation for adverse events beyond payments for medical expenses related to participation in the study is routinely offered. The Study Director and others involved in this study may be LSU employees. As employees of the University, they are protected under State Law, which limits financial recovery for negligence.

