#### **8.5. Safety Reporting Procedures**

All adverse events and serious adverse events should be reported. Depending on the nature of the event the reporting procedures listed below should be followed. Any questions concerning adverse event reporting should be directed to the chief investigator in the first instance.

All adverse events should be recorded on the Adverse Event Record Form (Appendix 5) and Adverse Event Monitoring Questionnaire (Appendix 6) and entered into a log. All data should be kept securely and to maintain confidentiality. All adverse events will be reported to the sponsor, Livful Inc. Depending on the nature of the event the reporting procedures below should be followed, see Appendix 7.

Regardless of the relation of the adverse event to study participation, the event must be reported as a serious adverse event if it meets any of the definitions in section 7.2. AE questionnaires meeting the SAE definition will be submitted to the medical monitor within 24 hours. SAEs that are assessed by the Study Director as being both related and unexpected must be reported to the LSU IRB within 15 days of the Study Director becoming aware of the event.

In the case of a severe reaction such as anaphylaxis, it will be treated as an emergency and an ambulance will be called immediately by dialling 911 directly from a mobile. In addition, a trained First Aider will be called.

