## 11.6. Appendix 6: Adverse Event Monitoring Questionnaire

To be completed by person who experienced the Adverse Event	
Name (first name SURNAME)	
Date of birth dd/mm/yyyy	
Phone number	
Mobile number	
E-mail address	
What kind of adverse event did you experience? e.g. skin rash, burning sensation, severe allergic reaction	
How long did the adverse event last?	
How serious was the event? mild / moderate / severe / life threatening	
Did you take any action to resolve the event?	
Was any treatment required?	
Did you visit A&E? Please enter details	
Did you stay in hospital overnight? Please enter details (no. nights/admission)	
Outcome unresolved / resolved / resolved with sequel	
To be completed by arctec trial manager	
Subject ID	
Study title	

Study code	
Type of study e.g. repellent, impregnated clothing, after-bite cream	
Exposure type e.g. chemical, mosquito bites, bed bug bites	
Exposure area e.g. forearm, legs	
Active ingredient	
Report date dd/mm/yyyy	
Other event Please enter details	
Likelihood of Adverse Event being related to study unrelated / unlikely / possible / probably / definite	
Serious Adverse Events	
Was the event serious? yes / no	
Admitted to Intensive Care Unit? yes / no	
Seriousness criteria (please tick)	
life threatening	
required hospitalisation	
prolonged hospitalisation	
congenital anomaly	

disabling/incapacitating	
important medical event	
required intervention to prevent impairment or damage	
Fatal	
If fatal, date of death  dd/mm/yyyy	
Primary cause of death	
Was a post-mortem performed?  yes / no	
Date adverse event become serious  dd/mm/yyyy	
Possible contributing factors to SAE other than study participation or underlying disease being studied  Please give details	
None apparent	
Concurrent illness, disease or other external factors	
Concurrent medication	
Study procedure	
Accident, trauma, or other external factors	
Other	
Relevant concomitant medication at time of SAE  yes / no – if yes please provide details	
Treatments/procedures for SAE  yes / no – if yes please provide details	

Relevant medical history (include only relevant past or concurrent medical disorder, surgeries, etc that might help explain the SAE)
 
yes / no – if yes please provide details
	

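### Section 8.1 gives relatedness to the medical monitor, but the 15-day IRB report depends on the Study Director alone, and the Appendix 6 footer names another assessor and another committee

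*Protocol*

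**What the plan says.** Three places in the protocol bear on who decides relatedness for expedited reporting.

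- **Section 8.1 (Medical Monitor).** When an adverse event occurs, "they will be asked to review the information provided and determine the severity and relatedness of the event". The task is to determine, not to advise.
- **Section 8.5 (Safety Reporting Procedures).** "AE questionnaires meeting the SAE definition will be submitted to the medical monitor within 24 hours". The next step depends on another person: "SAEs that are assessed by the Study Director as being both related and unexpected must be reported to the LSU IRB within 15 days", counted from when the Study Director learns of the event.
- **Appendix 6, footer of the questionnaire.** The duty appears again with the same 15-day limit, but the assessor is the CI and the recipient is the LSHTM ethics committee.

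Section 9.1 names the LSU board as the one responsible for approval and continuing review. Section 9.2 adds a general duty to document adverse events and report them under GLP and the board's procedures.

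**The concern.** The expedited report is the only route in the protocol with a fixed deadline for bringing a related, unexpected SAE to the ethics board. Its trigger is one person's judgement. That person is not the one to whom 8.1 gives the judgement. Section 8.5 sends the SAE questionnaire to the monitor within 24 hours, but its text does not make the monitor's conclusion count towards the trigger.

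The form that staff fill in for each event then tells them to send the report to a different committee. The subjects are healthy volunteers who, by section 3.2, gain no direct benefit. What could be lost is prompt independent review of an SAE that a designated assessor has already called related.

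**Working it through.** No figure in the plan is at issue, so the check sets the passages side by side.

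| Place | Who judges relatedness | What follows | Recipient |
|---|---|---|---|
| 8.1 | Medical monitor | No reporting step stated there | None stated |
| 8.5 | Study Director | 15-day report if related and unexpected | LSU IRB |
| Appendix 6 footer | CI | 15-day report if related and unexpected | LSHTM ethics committee |
| 9.1 | Not addressed | Approval and continuing review | LSU IRB |
| 9.2 | Not addressed | General reporting, no deadline given | Under IRB procedures |

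**Step 1: the trigger.** Take an SAE that is unexpected, and let the monitor and the Study Director each judge it related or not. That gives 2 × 2 = 4 combinations.

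| Monitor | Study Director | 15-day report under 8.5 as written | Report if either judgement triggers |
|---|---|---|---|
| Related | Related | Yes | Yes |
| Not related | Related | Yes | Yes |
| Related | Not related | **No** | **Yes** |
| Not related | Not related | No | No |

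The text of 8.5 requires the report in 2 of the 4 combinations, and an either-assessor rule requires it in 3. The only difference is the case in which the monitor's determination under 8.1 has no effect on the deadline.

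**Step 2: the recipient.** The footer differs from 8.5 and 9.1 even when everyone agrees that the event is related. Staff who follow the form would report to LSHTM, and nothing on the form sends them to LSU.

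**Step 3: the forms.** Section 8.5 requires both forms for every event. Appendix 5 asks about relation to the product. Appendix 6 asks how likely a relation to the study is. A reaction to a mosquito bite could properly be a no on the first and definite on the second. The two answers are compatible, but the forms do not say which one the word related in 8.5 refers to.

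**The case against.** The best defence is that 8.1 and 8.5 describe a sequence: the questionnaire reaches the monitor within 24 hours, the monitor gives a view, and the Study Director then makes the regulatory decision. The monitor is a round-the-clock nurse telephone line, so the sponsor may well have wanted the Study Director to decide. That reading is possible, but 8.1 has the monitor determine relatedness, and neither section says whose view prevails.

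Three further points limit the finding.

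- **Appendix 7.** Section 8.5 points to a safety-reporting flowchart of which only the heading is available. It may set an order of assessors or a threshold for related, so this review does not claim that none exists. It cannot remove the conflict between the visible texts.
- **Section 9.2.** A reader might infer that a related SAE could fail to reach the board at all. The general reporting line there, and the duty in 8.5 to report all events to the sponsor, do not support that. Only the 15-day report is exposed.
- **The CI.** This may be the Study Director under another title. If so, the footer's assessor agrees with 8.5, but its committee still does not.

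A reader might also infer a wider conflict, with several assessors and two scales for one judgement. The documents do not support this.

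- Section 8.4 says "The Sponsor, Medical Monitor, and Study Director will determine whether the injury is related", but only to decide payment of medical expenses.
- The Appendix 6 heading "To be completed by arctec trial manager" says who fills in the section, and the manager may be recording another person's judgement.
- The five levels "unrelated / unlikely / possible / probably / definite" answer a different question from the three-way item in Appendix 5.

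Nor can the effect be stated as a shift in a related-event rate. Section 7.2 plans a tabulation of adverse events without a split by relatedness, and a denominator of all exposed subjects would include untreated controls, who cannot have a product-related event.

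**Conclusion.** The point holds in a limited form. Section 8.1 and section 8.5 give the relatedness judgement to different people without ranking them, and the Appendix 6 footer names a committee other than the board responsible under 9.1. The consequence is confined to the 15-day report of unexpected SAEs. It can be missed when the monitor says related and the Study Director does not, and it can be misdirected when staff follow the form.

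The documents give neither an SAE rate nor a disagreement rate, so no probability can be attached. SAEs are likely to be rare in a study that the Study Director classes as low-risk. The change is still worth making because it protects volunteers and costs almost nothing. The conclusion rests on the visible text and assumes that the Appendix 7 flowchart does not already make the monitor's judgement a trigger. If it does, 8.5 and the footer still need to be brought into line with it.

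**What to change.** 1. Reconcile 8.1, 8.5 and the Appendix 6 footer, and check all three against the Appendix 7 flowchart.
2. Record the medical monitor's and the Study Director's relatedness assessments separately. Section 8.1 gives the monitor severity and relatedness only, so add expectedness to the monitor's task.
3. In 8.5, require the 15-day report to the LSU IRB when either assessor judges the SAE related and unexpected.
4. Correct the footer to name the Study Director and the medical monitor as assessors and the LSU IRB as recipient.
5. State on the forms that Appendix 5 records relation to the product, that Appendix 6 records relation to study participation, and that the Appendix 6 item governs IRB reporting.

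Section 8.4 can stay as it is. The cost is a few sentences of protocol text and small edits to two forms, with no added staff, visits or subjects. The downside is an occasional SAE report that the Study Director alone would not have sent.
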